### 5.3 Risk Assessment

This is the first study in human subjects with AMG 890. The assessment of potential side effects is based on the pre-clinical studies conducted to date (Section 5.2.3) and the literature. Overall, safety data from the nonclinical studies support the proposed doses and dosing schedule in this FIH study.

Earlier therapeutic antisense oligonucleotide molecules relied on numerous phosphorothioate backbone modifications to increase metabolic stability and increase gene silencing effectiveness (Chi et al, 2017). However, such modifications have also been shown to elicit strong platelet activation, aggregation and thrombus formation (Flieri, 2015). The affinity of the phosphorothioate backbone for various cellular proteins also affects certain pathways, such as inhibition of the intrinsic coagulation pathway and activation of the alternative pathway of complement (Farman and Kornbrust, 2003; Henry et al, 2002). The most concerning proinflammatory changes seen in animal models include glomerulonephritis and vasculitis. These effects seem to relate to high doses and plasma exposures (Engelhardt et al, 2015). AMG 890 is a double strand siRNA of a novel generation, which contains a majority of phosphodiester backbone linkages and 2'-fluoro and 2'-methoxy nucleotide chemical modifications. In general,

these modifications provide enhanced resistance to degradation, lower toxicity and increased hybridization affinity (Judge et al, 2006; Wu et al, 2014; Crooke et al, 2016). Furthermore, the tri-N-acetylgalactosamine (NAG) moiety conjugated to 1 of the siRNA strands directs trafficking of AMG 890 to hepatocytes and mediates its internalization via the high affinity ASGPR, which may allow the use of lower effective doses and lower exposures (Chen et al, 2018). Therefore, the risks associated with earlier antisense oligonucleotides such as platelet and complement activation, and proinflammatory changes are considered low for AMG 890. In addition, organ toxicity related to intracellular accumulation and off-target effects of the siRNA are not expected at the doses administered. (Chi et al, 2017; Janas et al, 2018). Injection site reactions, hypersensitivity reactions, including anaphylaxis, and development of anti-drug antibodies (ADAs) are considered potential risks.

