To minimize risk, a sentinel dosing strategy will be adopted for cohorts 1 to 5, and safety data will be reviewed in an accumulative manner during dose level review meetings (DLRM) prior to progressing to the next dose level in the study. Specific cohort dose stopping rules are specified in this protocol (Section 9.2.4). All study subjects will be closely monitored and frequently assessed for adverse events throughout the study. The laboratory safety monitoring includes evaluation of routine chemistry (including bicarbonate/CO2 and liver function tests), hematology, and coagulation assessments. Lactate will be measured reflexively in the presence of an anion gap metabolic acidosis. Potential anaphylactic reactions will be assessed by Sampson criteria (Sampson et al, 2006). If Sampson criteria are positive, the potential anaphylactic reaction will be confirmed by measuring tryptase in blood plasma within 30 minutes of symptoms, if feasible. Bioanalytical testing for anti-AMG 890 antibodies will be conducted only if there are unexpected PD findings or a safety signal in this study or future studies that warrants further investigation. Additional blood samples may be obtained to rule out anti-AMG 890 antibodies during the study.

New onset or worsening neuropathy were reported during the clinical development program of an siRNA for the treatment of hereditary transthyretin amyloidosis. Neuropathy events have not been described in other recent human studies of antisense-based therapies (Chi et al, 2017), and safety pharmacology non-human primate studies did not disclose any evidence of neurologic effect of AMG 890 at all tested doses up to 150 mg/kg, the highest tested dose. However, clinical neurologic assessments are part of the safety evaluations throughout this study. If treatment

emergent neuropathy is suspected, dosing will be suspended and subjects will be directed to a specialist for further evaluation.

Low levels of Lp(a) have been associated with increased prevalence of type 2 diabetes mellitus (reviewed in Paige et al, 2017). There is uncertainty about the strength of this association, and available evidence does not suggest a causal link (Ye et al, 2014). Some evidence suggests that the hyperinsulinemia present in type 2 diabetes may lead to lower Lp(a) levels (Purnell et al, 1995; Neele et al, 1999). Fasting blood glucose will be monitored throughout the study.

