**13.5.2 Primary Endpoint(s)**

**13.5.2.1 Safety Endpoint(s)**

**13.5.2.1.1 Adverse Events**

All subjects who receive a dose of AMG 890 or placebo in the safety analysis set will be included in the analysis of the primary endpoints. Subject incidence of all treatment-emergent adverse events will be tabulated by system organ class and preferred term according to the medical dictionary for regulatory activities (MedDRA) terminology. Tables of fatal adverse events, serious adverse events, adverse events leading to withdrawal from IP or other protocol-required therapies, and significant treatment emergent adverse events will also be provided if observed. The number and percentage of subjects reporting adverse events will be evaluated for each dose cohort and across dose cohorts.

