9.6 Safety Analyses

9.6.1 Adverse Events and Disease-related Events

The Medical Dictionary for Regulatory Activities (MedDRA) version 25.0 or later will be used to code all events categorized as adverse events to a system organ class and a preferred term.

Subject incidence of adverse events will be summarized for all treatment-emergent adverse events, serious adverse events and fatal adverse events by treatment group and cohort during the treatment period.

Severity of adverse events are graded as Mild, Moderate and Severe.

If a subject experienced multiple TEAEs with the same preferred term, this will be counted as separate TEAEs for that treatment under each specific severity recorded.

Summaries of treatment-emergent adverse events, serious adverse events and fatal adverse events during the treatment period will also be tabulated by system organ class, preferred term.

Summary of treatment-emergent adverse events by preferred term and by severity will be tabulated.

SAEs during the follow-up- period will be tabulated by system organ class and preferred term for each treatment group and cohort (cohorts 1-7 only).

Details of each adverse event will be reviewed. Listings of any on-study deaths, serious adverse events (SAE), and events leading to withdrawals of IP or other protocol-required therapies will be reviewed.

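### The significant-TEAE table promised in the protocol is missing from the SAP without being declared, and the planned tables need not show how many distinct subjects had a named harm coded to several preferred terms

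*SAP*

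**What the plan says.** **The harms of concern.** Protocol 5.3 states: "Injection site reactions, hypersensitivity reactions, including anaphylaxis, and development of anti-drug antibodies (ADAs) are considered potential risks". The same section takes up neuropathy separately: "New onset or worsening neuropathy were reported during the clinical development program of an siRNA", and for that reason "clinical neurologic assessments are part of the safety evaluations throughout this study". Neuropathy is therefore a monitored concern and not an item in the list of potential risks.

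**What the protocol promises.** Protocol 13.5.2.1.1 plans subject incidence by system organ class (SOC) and preferred term (PT), with further tables of fatal events, serious events and events leading to withdrawal. It adds that tables of "significant treatment emergent adverse events will also be provided if observed". On level of summary it says: "The number and percentage of subjects reporting adverse events will be evaluated for each dose cohort and across dose cohorts".

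**What the SAP plans.** SAP 9.6.1 gives overall incidence of all treatment-emergent events, "serious adverse events and fatal adverse events by treatment group and cohort during the treatment period". It then says that summaries of the same three categories "during the treatment period will also be tabulated by system organ class, preferred term". It adds: "Summary of treatment-emergent adverse events by preferred term and by severity will be tabulated". Serious events in the follow-up period get an SOC and PT table for cohorts 1 to 7. Event details and some listings are to be reviewed.

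**What the SAP leaves out.** SAP 9.6.1 has no table of significant events and no grouped category or term list, and SAP Section 5 defines none. SAP Section 10 declares one change only, the removal of the analysis of events leading to withdrawal of investigational product.

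**The concern.** Safety and tolerability is the primary objective, and subject incidence of treatment-emergent events is a primary endpoint. For a harm the protocol singles out, the natural question is how many subjects in each cohort had it. An injection-site reaction, a hypersensitivity reaction or a neuropathy can each be recorded under more than one PT, and one subject can appear under several of them. PT rows then cannot be added to give a subject count. The SOC row counts subjects once but can include unrelated events.

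The table of significant events is where such a count could have gone. It is missing, and the section meant to record departures from the protocol does not mention it. Without a prespecified grouping, a class count would have to be made by hand, with the list of terms chosen after the events are known.

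**Working it through.** **Step 1. The plan's own figures.** SAP 3.2 gives the chance of seeing at least one subject with an event of true incidence p among n subjects, which is 1 − (1 − p)^n.

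- n = 6, p = 0.20: 1 − 0.8^6 = 0.738 (stated 74%).
- n = 10, p = 0.20: 1 − 0.8^10 = 0.893 (stated 89%).
- Overall, the number on AMG 890 is blacked out in the text. Table 1 gives 5 × 6 + 2 × 9 + 2 × 6 = 60. With p = 0.05: 1 − 0.95^60 = 0.954 (stated 95%).

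All three reproduce. The formula scores each subject once, as having the event or not. If the event of interest is a class, the matching observed quantity is the number of distinct subjects with any term in that class.

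**Step 2. Planned outputs, protocol 13.5.2.1.1 against SAP 9.6.1 and Section 10.**

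- All treatment-emergent events by SOC and PT: in both.
- Serious and fatal events: in both.
- Events leading to withdrawal: in the protocol; Section 10 removes the analysis and gives a reason (SAP 9.6.1 keeps a listing for review).
- Significant treatment-emergent events: in the protocol, conditional on occurrence; absent from SAP 9.6.1 and not mentioned in Section 10.
- PT by severity: added in the SAP; still term by term.

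**Step 3. What PT rows say about distinct subjects.** Let a class appear as PT rows with subject counts c1, …, ck in a cohort of n. The number of distinct subjects D satisfies

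max(c) ≤ D ≤ min(n, sum of c).

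The lower limit is reached when the same subjects account for the smaller rows, the upper when no subject appears twice. The row patterns below are illustrations; the cohort sizes on AMG 890, 6 and 9, are from Table 1.

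- n = 6, rows 2, 2, 1: D from 2 to min(6, 5) = 5, that is 33% to 83% of the cohort.
- n = 6, rows 1, 1, 1, 1: D from 1 to min(6, 4) = 4, that is 17% to 67%.
- n = 9, rows 2, 2, 2: D from 2 to min(9, 6) = 6, that is 22% to 67%.

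**Step 4. Whether another planned table resolves it.** The SOC row does so only if all terms of the class fall in one SOC and nothing unrelated is reported there in that cohort. Otherwise it gives at most a further upper limit. The severity table is by PT, and a subject with repeated events of one term is counted under each severity recorded, so it does not help. Overall incidence covers all events together. If the harm falls under a single PT, k = 1 and the row gives D exactly.

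**The case against.** **The tables follow the protocol.** SOC and PT is what the protocol specifies, and neither document mentions grouped searches. The promised table is conditional, *significant* is undefined, and nothing ties it to these classes. All true. Restoring the title alone would not produce the counts; the classes and their terms must also be defined.

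**Collection limits fragmentation.** Protocol 12.2.1.1 asks for a diagnosis or syndrome where known. Suspected neuropathy goes to a specialist, and suspected anaphylaxis is judged against set criteria. This makes a single term more likely for those two harms, so the gap may turn out small. It does not rule out several terms.

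**A manual count is easy.** With 6 to 9 subjects on AMG 890 per cohort and event details reviewed, anyone with subject-level data can count. That stands: the information is not lost. But a hand count fixes neither the grouping nor its reporting in advance.

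**A reader might infer that the tables understate the incidence of these harms.** They do not. PT rows state PT incidence correctly. If each affected subject has one term, the rows add exactly to the class total; if some have several, the sum overstates it. How thinly a class spreads over rows depends on terms per subject and their relative frequency, which the documents do not give, so no dilution figure is offered.

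**A reader might also infer that safety monitoring is weakened.** The documents do not support that. The Dose Level Review Team reviews all adverse events, and the stopping rules in protocol Table 3 do not work through PT tables.

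**Conclusion.** The point holds as a cheap improvement to the primary safety output. Two facts rest on the text alone: the protocol's table of significant events is absent from SAP 9.6.1, and SAP Section 10 does not declare its removal. The consequence is conditional. Where a named harm is coded to more than one PT, the planned tables need not show how many distinct subjects per cohort had it, and in a cohort of 6 the uncertainty can run from 2 to 5 subjects. That range rests on an illustrative row pattern and not on a forecast of how events will be coded.

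It would go too far to say that the SAP drops a promised analysis of these particular harms, since the protocol never links its table to them, or that neuropathy is one of the listed potential risks. The point concerns table layout and prespecification, not clinical management.

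**What to change.** Add to SAP 9.6.1 one subject-incidence table by treatment group and cohort, with placebo pooled as SAP 9.1 sets out, counting each subject once per class:

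- injection-site reactions;
- hypersensitivity, including anaphylaxis;
- peripheral neuropathy.

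Define each class by a MedDRA high-level term or standardised query, and print the term list under the table. Protocol 13.3 keeps the medical monitor unblinded throughout and lets sponsor staff receive assignments when needed. The lists should therefore be fixed before final database lock and without reference to treatment assignment.

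Then either state in SAP 9.6.1 that this table defines the significant treatment-emergent events of protocol 13.5.2.1.1, or record in Section 10 that the protocol's table is dropped and why. Hepatic and glucose-related groups are optional, because those laboratory values are already summarised by cohort and time point under SAP 9.6.2.

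The cost is a few lines of SAP text and one more table from events already collected and coded. Broad groupings may draw in a few non-specific terms, which is the reason to print the lists.

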## 6.5 Estimated Study Duration

### 6.5.1 Study Duration for Subjects

Subject participation will vary according to enrollment scheme. The duration of the follow-up period for each cohort was defined based on the simulation results from the population K-PD model describing the Lp(a) response to AMG 890 administration developed based on 57-day GLP repeat-dose cynomolgus monkey toxicology and PK/PD studies (Section 5.2.1). Data suggest that the lengths of study participation proposed will allow plasma Lp(a) levels to return at least to 80% of the baseline levels for each subject after administration across the proposed AMG 890 clinical doses.

For cohorts 1 and 2, planned subject participation will last up to 141 days, including a 28-day screening period prior to investigational product (IP) administration and on-study period (through the end of treatment visit) lasting 113 days.

For cohorts 3 to 7, planned subject participation will last up to 253 days, including a 28-day screening period prior to IP administration and on-study period (through the end of treatment visit) lasting 225 days.

For cohorts 8 and 9, planned subject participation will last up to 393 days, including a 28-day screening period prior to IP administration and on-study period (through the end of study visit) lasting 365 days.

For cohorts 1 to 7, the end of treatment visit will complete the subject's participation in this study unless a follow-up period is required. If there is a clinically significant clinical or laboratory abnormality that requires monitoring, subjects will be followed until resolution of the abnormality or until it is considered stable.

For cohorts 1 to 9, if at the end of treatment visit, the plasma Lp(a) level has not returned to  $\geq 80\%$  of baseline (mean of screening and day 1 predose), the follow-up period will be required.

The end of treatment visit for cohorts 8 and 9 will be the same as the end of study visit (day 365).

Subjects in cohorts 1 and 2 will return to the clinical study site approximately every 2 weeks until the Lp(a) level returns to  $\geq 80\%$  of baseline. Assessments during the follow-up period will include physical examination; vital signs; and collection of blood samples for chemistry, hematology, lipid, Lp(a), and biomarker development. When the protocol amendment 2 is implemented, the follow-up visits will continue approximately monthly, as needed, and will include only Lp(a) monitoring as described below for cohorts 3 to 7.

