Subjects in cohorts 3 to 7 will return to the clinical study site for Lp(a) monitoring approximately monthly starting from when the site has been notified of the Lp(a) follow-up requirement until the Lp(a) level returns to  $\geq 80\%$  of baseline.

Lp(a) assessments in the follow-up period will be performed by Medpace.

**Primary Completion:** The primary completion date is defined as the date when the last subject is assessed or receives an intervention for the final collection of data for the primary endpoint(s), for the purposes of conducting the primary analysis, whether the study concluded as planned in the protocol or was terminated early.

The primary completion date is the date when the last subject has completed the assessments for day 365 of cohort 9.

If the study concludes prior to the primary completion date originally planned in the protocol (ie, early termination of the study), then the primary completion date will be the date when the last subject is assessed or receives an intervention for evaluation in the study (ie, last subject last visit).

**End of Study:** The end of study date is defined as the date when the last subject is assessed or receives an intervention for evaluation in the study (ie, last subject last visit), following any additional parts in the study (eg, follow-up period; long-term follow-up), as applicable.

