#### **12.2.1.3      Serious Adverse Events after the Protocol-required Reporting Period**

There is no requirement to monitor study subjects for serious adverse events following the protocol-required reporting period or after end of study. However, these serious adverse events should be reported to Amgen (regardless of causality) if the investigator becomes aware of them. Per local requirements in some countries (eg, European Union [EU] member states), investigators are required to report serious adverse events that they become aware of after end of study. If serious adverse events are reported, the investigator is to report them to Amgen within 24 hours following the investigator's knowledge of the event.

Serious adverse events reported outside of the protocol-required reporting period will be captured within the safety database as clinical trial cases for the purposes of expedited reporting.

**If further safety related data is needed to fulfill any regulatory reporting requirements for a reportable event, then additional information may need to be collected from the subject's records after the subject ends the study.**

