Randomization date is defined as the date subject was allocated a unique randomization number and assigned to either AMG 890 or placebo group.

Study Day 1

defined as the first day that investigational product is administered to the subject.

Study Day

Post study day 1: study day= (date of event-study day 1) +1

Pre-study day 1: study day= (date of event-study day 1)

Treatment-emergent Adverse Event during Treatment Period

A treatment-emergent adverse event during treatment period is any adverse event starting on or after the first dose of investigational product (as determined by the flag indicating if the adverse event started prior to the first dose or not on the Adverse Events eCRF) and up to and including the End of Treatment Date, **or EOS date for subjects who early discontinue the study during the treatment period.**

Treatment-emergent Serious Adverse Event during Follow-up Period

Subjects in cohorts 1-7 will be followed up for SAE reporting (every 2 weeks for cohorts 1-2 and monthly for cohorts 3-7) if the Lp(a) level has not returned to $\geq 80\%$ of baseline by the end of treatment visit. SAEs during the follow-up period are defined as any serious adverse event **categorized as Adverse Events (AEs) starting on or after first dose of investigational product (as determined by “Did event start before first dose of investigational product” equal to No or missing on the Events eCRF) and starting on or after the end of treatment date and up to and including the end of study date for an individual subject.**

If end of treatment and end of study is same for a subject, then the subject will only have TEAEs for treatment period derived.

For subjects in Cohort 8 and 9 the end of treatment and end of study is same i.e. day 365 so for those cohorts only TEAEs for treatment period will be derived.

6. Analysis Sets

For all analyses, subjects will be analyzed according to the dose and treatment they received, not the dose and treatment to which they were randomized.

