9.1 General Considerations

Descriptive statistics will be provided for selected demographics, adverse events, vital signs, ECG and selected laboratory measurements. Descriptive statistics on continuous measurements will include means, medians, standard deviations, and ranges, while categorical data will be summarized using frequency counts and percentages. Data will be presented and summarized by treatment group and cohort at each scheduled time point. Graphical summaries of the data may also be presented.

Data for subjects receiving placebo will be combined across cohorts 1 to 5 and separately across cohorts 6 to 9.

When data are summarized by time, the values recorded against the scheduled time points listed in the protocol will be used. When assessing minimum/maximum increases or decreases over the study, all assessments, including unscheduled assessments will be used. Unless stated otherwise in the statistical analysis plan, the data analysis will be conducted using subjects in the safety analysis set. For statistical analyses comparing change from baseline, only subjects with both baseline and at least one post-baseline assessment will be included.

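### Cohorts 1-7: entry to SAE follow-up after end of treatment depends on Lp(a) response, but the follow-up SAE table has no stated denominator and by default counts unfollowed subjects as event-free

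*SAP*

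**What the plan says.** **Entry.** SAP Section 5, under the definition of treatment-emergent SAEs in the follow-up period: "Subjects in cohorts 1-7 will be followed up for SAE reporting (every 2 weeks for cohorts 1-2 and monthly for cohorts 3-7"), and this applies "if the Lp(a) level has not returned to" at least 80% of baseline by the end of treatment visit (day 113 for cohorts 1 and 2, day 225 for cohorts 3 to 7). Protocol 6.5.1 continues the visits until that level is regained.

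**Everyone else.** Protocol 6.5.1: "For cohorts 1 to 7, the end of treatment visit will complete the subject's participation in this study unless a follow-up period is required". SAP Section 5 adds: "If end of treatment and end of study is same for a subject, then the subject will only have TEAEs for treatment period derived". Protocol 12.2.1.3: "There is no requirement to monitor study subjects for serious adverse events following the protocol-required reporting period or after end of study".

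**Table.** SAP 9.6.1: "SAEs during the follow-up- period will be tabulated by system organ class and preferred term for each treatment group and cohort (cohorts 1-7 only"). No denominator is given.

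**Default.** SAP 9.1: "Unless stated otherwise in the statistical analysis plan, the data analysis will be conducted using subjects in the safety analysis set". The same section summarises categorical data as counts and percentages, and pools placebo over cohorts 1 to 5 and, separately, over cohorts 6 to 9.

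**Bias.** SAP 8.4 undertakes to note sources of bias, including informative censoring, in the clinical study report.

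**The concern.** The entry rule is not written by arm, but it selects on a post-dose measurement that the drug is designed to lower. Within one randomised cohort, AMG 890 subjects with persisting response stay under observation. Most placebo subjects, and AMG 890 subjects who have recovered, leave at end of treatment. A subject who has left cannot contribute a follow-up SAE under the SAP's own derivation, yet remains in the safety set.

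Followed as written, the plan puts a percentage under each treatment group that mixes subjects observed without an event and subjects not observed at all. A low or zero placebo percentage could then be read as absence of SAEs when it mostly reflects absence of observation. The AMG 890 percentages are diluted too, by an amount that differs between dose cohorts according to how many subjects have recovered.

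**Working it through.** **1. The plan's own figures.** The documents give no figure for follow-up SAEs. The only safety-detection figures with an unredacted n are those in SAP 3.2, using 1 − (1 − p)^n:
- n = 6, p = 0.20: 1 − 0.8^6 = 73.8% (stated 74%).
- n = 10, p = 0.20: 1 − 0.8^10 = 89.3% (stated 89%).

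Both reproduce. They presuppose that all n subjects are observed, which is the condition that fails in the follow-up period.

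**2. Planned numbers (SAP Table 1).**
- AMG 890, cohorts 1-7: 5 × 6 + 2 × 9 = 48.
- Placebo, cohorts 1-7: 5 × 2 + 2 × 3 = 16.
- Placebo columns as pooled in SAP 9.1: cohorts 1-5, 5 × 2 = 10; cohorts 6-9, 3 + 3 + 2 + 2 = 10. Four of the latter are in cohorts 8-9, for which SAP Section 5 derives no follow-up period.

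**3. Effect of the denominator.** Printed percentage = events / N dosed. Percentage among those observed = events / n followed. The ratio of the two is n followed / N dosed, whatever the event rate.

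| Column | Followed (illustrative) | One SAE, safety set | One SAE, followed subjects |
|---|---|---|---|
| Cohort 7 AMG 890, N = 9 | 6 | 1/9 = 11% | 1/6 = 17% |
| A 6-subject AMG 890 cohort | 3 | 1/6 = 17% | 1/3 = 33% |
| A 6-subject AMG 890 cohort | 2 | 1/6 = 17% | 1/2 = 50% |

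If no placebo subject is followed, placebo over cohorts 1-7 prints as 0/16 = 0%. Taken at face value, that carries a one-sided 95% upper limit of 1 − 0.05^(1/16) = 17.1%. With followed subjects as denominator it is 0/0, not estimable.

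**4. How many placebo subjects would be followed.** Baseline Lp(a) is the mean of two values, screening and day 1 predose. The within-subject CV is not in the documents; 5-15% is assumed. Take independent normal values around a stable mean of 1. The subject enters if X − 0.8 × B < 0, where B is the mean of two values. This difference has mean 0.2 and variance CV² × (1 + 0.64/2) = 1.32 × CV², so P(enter) = Φ(−0.2 / (CV × √1.32)).

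| CV | z | P(enter) | Expected of 16 | P(at least one of 16) |
|---|---|---|---|---|
| 5% | −3.48 | 0.025% | 0.00 | 0.4% |
| 10% | −1.74 | 4.1% | 0.65 | 49% |
| 15% | −1.16 | 12.3% | 1.97 | 88% |

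A lognormal version, with SD of the log ratio σ√1.5 and σ² = ln(1 + CV²), gives 0.01%, 3.4% and 11.1%. Either way about 0 to 2 of 16 placebo subjects are followed, so 14 or more are not.

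**The case against.** The strongest reply is about reach. The study is descriptive and plans no test between arms. The primary analysis uses data only up to each subject's end of treatment visit (SAP 7.2). The treatment-period adverse event, SAE and fatal event tables use a window fixed by cohort, not by Lp(a), and follow-up is summarised only at the final analysis (SAP 7.3). SAE listings are reviewed as well. All of this stands: one supplementary table is affected.

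SAP 8.4 already promises that informative censoring will be noted in the study report. That covers part of the footnote proposed below, but it changes neither the denominator nor what the table prints.

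The safety-set denominator is inferred from the 9.1 default, and SAEs per subject dosed is a legitimate quantity. Both points are fair. The percentage is not arithmetically wrong; it answers a different question from the one a table of follow-up SAEs by arm invites. If followed subjects were intended, the SAP needs to say so, because its default says otherwise.

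Protocol 6.5.1 also says participation lengths were chosen, from a model built on monkey data, so that Lp(a) would return to at least 80% of baseline for each subject. If that holds, few AMG 890 subjects enter follow-up, and the full-cohort denominator is then further from the number observed.

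Three stronger readings are tempting but not supported:
- *Placebo is certain to show 0% unobserved.* The rule can admit a placebo subject by chance; at CV 10-15% the chance that at least one of 16 enters is 49-88%. Largely unobserved is the accurate description.
- *The placebo column will include cohorts 8-9.* The restriction to cohorts 1-7 in 9.6.1 probably overrides the general pooling rule. The text leaves the possibility open, no more.
- *Relatedness judgements are biased because sites learn who is responding.* Protocol 6.5.1 has visits "starting from when the site has been notified of the Lp(a) follow-up requirement", but a placebo subject can trigger that notice too, and 9.6.1 plans no follow-up SAE table by relatedness. The documents do not establish such a bias.

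**Conclusion.** The concern holds for the follow-up SAE table in cohorts 1-7. Entry depends on the drug's own effect, subjects not followed cannot contribute an event, and the only denominator rule in the SAP keeps them in. The denominator effect needs no assumption beyond the number followed: the printed figure is the followed-subject figure multiplied by the fraction followed, as in 11% against 17% for cohort 7 with 6 of 9 followed. The estimate that about 0 to 2 of 16 placebo subjects are followed rests on an assumed CV of 5-15%, stable placebo Lp(a) and independent normal errors. The share of AMG 890 subjects followed, their time in follow-up and the background SAE rate are not in the documents, so no probability of a spurious imbalance is claimed.

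A reader might infer that the primary safety assessment is compromised. It is not: the treatment-period tables do not use this rule. The correction is still worth making before the final analysis, because the default as written yields percentages by arm that mislead.

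**What to change.** In SAP 9.6.1, for the follow-up SAE table:

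1. Set the denominator to subjects who entered follow-up, defined as an end of study date later than the end of treatment date.
2. Show the number entered and total subject-days of follow-up in each column.
3. State that placebo comes from cohorts 1-7 only, so that the 9.1 pooling over cohorts 6-9 cannot add the 4 planned placebo subjects of cohorts 8-9, who have no follow-up period in SAP Section 5.
4. Where nobody in a column was followed, print n entered = 0 instead of 0%.
5. Footnote that entry depends on Lp(a) response, so the columns are not a randomised comparison, consistent with SAP 8.4.

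The cost is SAP wording and one table shell. The dates are already defined and collected, and trial conduct does not change. The downside is that the table cannot be used to compare arms, and some columns will rest on very few subjects.
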